- Week 8: Course Review. In this session, students will reflect on the course, the instructor will provide additional resources, and participants will discuss their experiences with the group.

Subsection 2.13 - Phase II Health Promotion Intervention

The Health Promotion program is eight weeks long with one 1.5-2 hour session per week (the seventh week has two sessions to ensure the same number of contact hours as the "mini-retreat" in the MBSR course). The Health Promotion Classes were designed to be analogous to the MBSR classes in terms of length and contact hours. This is because the effect of being in a group and participating in a study could help participants, without the benefit having much – if anything – to do with the actual intervention.

The program will be run by a UCI graduate or postbac student with a BA or higher. The SMART (Specific Measurable Achievable Relevant Time-based) framework will be used for goal setting. In this framework, specific, achievable goals are outlined by the participant as relevant to each class. This helps with information retention and helps reinforce concepts and positive behaviors. Snacks and drinks will be provided.

Each week in the Health Promotion program focuses on a different theme. The sessions are as follows:

- 1. Introduction & overview
- 2. Envisioning Health through Art
- 3. Chronic Disease I Heart Health
- 4. Chronic Disease II Diabetes
- 5. Nutrition and Hydration
- 6. Infectious Disease Prevention
- 7. Skin Care
- 8. Oral Health
- 9. Promoting Social Integration & Course Graduation

Subsection 2.14 - Phase II Post-Assessment

After the ninth session (of either MBSR or Health Promotion), a post-assessment will be administered via tablet. Urine will again be collected to validate self-report drug use. Participants will repeat the brief stress task (Trauma Imagery Task) using an identical strategy and provide saliva samples before and after. The Lead Researcher or a postbac student researcher will be on site to answer any questions or clarify any items. Urine and saliva samples will both be stored in a freezer on-site or at [name] research office and then transferred to UCI for analysis within 36 hours. Follow-ups will occur on site unless participant has moved to sober living or other location. Zoom or phone will be implemented for those who moved out of state

Subsection 2.15 - Phase II Team Management of Biospecimen Collection Refusal

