Research staff will be trained to assess and react as follows:

RED FLAG – SUICIDE

During your work as a research staff, you may encounter a respondent who expresses suicidal intentions, or you may suspect that a respondent may be suicidal. Be sure to document all the information in sections I and II as you will need to provide that information to the treatment program counselor or on-call clinician.

- I. Is this person a suicide risk?
 - _____ The individual is currently thinking about suicide.
 - The individual has a plan and the means to commit suicide.
 - _____ The individual has attempted suicide in the past.

If any of the above are true or if you suspect the client is suicidal, also note if:

- The individual is currently exhibiting serious depression/anxiety.
- The individual is experiencing stressful life events.
- II. Assessment of support system:
 - a) Is the individual under professional care (i.e., psychologist, psychiatrist, counselor)?
 - b) Does the individual have a social support network (i.e., friends, family, sponsor)?
 - c) Has the individual talked with any of the members of his or her social support network in the last 30 days?
 - d) Is the individual able to talk about this issue with his or her support system?
 - e) Is the individual aware of available social service programs?
- III. If the person appears to be suicidal or has attempted suicide since the last interview:
 - a) Let the respondent know that you are concerned, and that you need to inform a clinician and your supervisor.
 - b) If you are not at a treatment program, have the client wait with you or hold on the line while you take the following steps:
 - If the client has indicated that he/she is under professional care, ask the client for permission to contact his/her clinician and, if permission is granted, obtain the clinician's contact information. Be sure to document the client's permission and clinician contact information, you will need to provide it to the on-call clinician who will confirm client permission and make the contact.
 - 2) Contact the on-call clinician at the Los Angeles County Mobile Crisis Response Team (MCRT); ______. A clinician is on call 24 hours a day. Provide the clinician with all the suicidality information you have gathered. Facilitate phone contact between your client and the MCRT clinicians. The clinician will make the decision about what steps to take with this client. Document the details of the clinician call.

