 - d) Report back to the PI immediately.
 - Your Principal Investigator [name], [contact]

The situation will be evaluated by the group and a decision will be made if it should be reported to the LAC MCRT; they will advise us on how we need to proceed.

- e) If the person attempts to harm himself or herself in your presence, contact the police (911). The police may place the person in a psychiatric facility for a 72-hour observational hold. Get the police report number.
- f) Complete an Incident Report detailing the problem and action taken. Be sure that the Incident Report is placed in the respondent's file.

g) Make arrangements to follow-up on your client's status with the treatment program counselor, supervising counselor, or on-call clinician within the next seven days.

If the MCRT is called, an assessment will be done by the MCRT staff at the location of the participant. Based on the assessment of the MCRT, the participant may be transported to a hospital for inpatient treatment. If it is determined that the person does not need to be hospitalized, the participant will be referred to the outpatient services at the neighborhood clinic. If the participant is at the same location as the staff, the staff will find out if the participant has taken any active steps such as already having taken pills, etc. If the participant is not in immediate danger, the staff will find out the following: history of drug and alcohol abuse; history of familial suicide; history of familial mental illness. The staff will find out if the participant has a plan for how he would commit suicide. If she does have a plan, the staff will find out if she/he has any weapons, pills, etc, and remove all weapons from her possession, and explore the nature of her various plans. The PI, once they have arrived, will continue to focus on the reasons the participant of those of his outside support system with whom he wishes to be in contact, for future use in case of another emergency. The research staff will collaborate with the treating psychiatrist to facilitate referral and follow through with a counseling psychiatrist/psychotherapist after discharge from the hospital. The staff/PC will document each step of this process.

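### The suicide steps shown for staff away from a treatment program name only a Los Angeles County crisis team and do not tell staff to confirm, or send help to, the location of a woman followed by Zoom or phone out of state

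*Combined protocol and SAP*

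**What the plan says.** Section 2.14 provides that "Zoom or phone will be implemented for those who moved out of state". Section 2.17 repeats the option for the 6-month follow-up, after saying that research staff will normally travel to the participant.

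The suicide procedure is in Appendix III under RED FLAG – SUICIDE. Item III(b) covers staff who are not at a treatment program and foresees telephone contact: "have the client wait with you or hold on the line while you take the following steps". Two steps follow. Step (1) asks permission to contact the woman's own clinician, if she has one; the on-call clinician then makes that contact. Step (2) reads "Contact the on-call clinician at the Los Angeles County" Mobile Crisis Response Team (MCRT), and continues: "Facilitate phone contact between your client and the MCRT clinicians". It adds: "The clinician will make the decision about what steps to take with this client". Item III(d) has staff report to the principal investigator at once.

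Item III(e) reads: "If the person attempts to harm himself or herself in your presence, contact the police (911"). The text after item III(g) says that, if the MCRT is called, "an assessment will be done by the MCRT staff at the location of the participant". The same text says: "If the participant is at the same location as the staff, the staff will find out if the participant has taken any active steps".

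On location data, Section 2.21 says that locator information is linked on REDCap, is available to research staff in real time, and is used to track women for follow-up. The suicide steps shown do not mention it.

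**The concern.** The follow-up rules let the study assess a woman who is in another state, while the off-site suicide steps are built around one county's crisis team and around staff being physically with the participant. If a woman discloses suicidal intent on such a call, staff who follow the printed steps have not been told to establish where she is or to reach a service that can get to her. Sending help would then depend on what the county clinician thinks to ask and is able to arrange.

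The event is foreseen. The monitoring plan lists suicide attempt as a possible serious adverse event, and the suicide procedure opens by warning staff that they may meet a suicidal respondent. Section 2.9 records that women in pilot work became distressed during the life-events inventory and the PCL. The documents do not say which procedures are done remotely. Since the PCL-5 is the primary outcome, a remote follow-up can be expected to include it; that is an inference.

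What is at stake is participant safety. Nothing here bears on the treatment comparison.

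**Working it through.** No formula applies and the plan gives no figure to reproduce. The check sets the follow-up rules beside the suicide steps and follows a remote call through them.

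1. **Can the situation arise?** Yes. Sections 2.14 and 2.17 both allow Zoom or phone for women who moved out of state. Staff on such a call who are not at a treatment program fall under III(b), and its hold-the-line wording shows that telephone contact was in view.

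2. **What reaches her by phone?** The Section I questions (current ideation, plan and means, past attempts) apply to everyone. An MCRT clinician, on call 24 hours a day, speaks to her and decides what to do. Her own clinician may be contacted with her permission. The principal investigator is told immediately.

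3. **Is her location established?** Not in the steps shown. Section I covers risk and Section II covers her support system; neither asks where she is. Step III(b)(2) has staff give the clinician the suicidality information they have gathered, which by those lists does not include location. The Locator Guide is described in Sections 2.2, 2.17 and 2.21 for keeping contact and tracking, and Section 2.2 lets it be filled in gradually. No link to it appears in the suicide steps.

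4. **Is a service covering her location reached?** The only crisis service named is the Los Angeles County MCRT, which assesses the participant in person. Contact with her own clinician needs an existing clinician and her consent, so it is not a dispatch route.

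5. **Do the backstops apply on a call?** The 911 instruction is tied to an attempt in the staff member's presence, which leaves Zoom unclear and says nothing of routing a call to another state. The sentence on steps already taken, such as pills, is conditioned on sharing a location with staff.

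Count over the steps shown: 2 are worded around physical presence (the 911 step and the check on steps already taken), and 0 tell staff to confirm a remote participant's location or contact an emergency service covering it. This is a count of wording and does not measure risk. The two printed copies of the protocol agree.

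**The case against.** The strongest reply is that a remote participant already has a live response: she is kept on the line, a crisis clinician speaks to her, and that clinician decides the next step and may well bring in local help. This stands in part. A reader might infer that the MCRT could not help a woman out of state, but the documents give no catchment or referral rules. That limit is an inference from the team's name and its on-location assessment. Equally, the documents do not say that it would arrange local help.

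Second, a reader might infer that the study does not know where she is. The documents do not support that: research staff have real-time access to locator data, and a remote call is used because she is known to have moved. What is missing from the steps shown is the link to those data and a check that they are current. The form itself was not available, so whether it holds a current address is unknown.

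Third, part of the text is not visible. The lettering runs from III(b) to III(d) in both copies, and some pages before the monitoring board text, the Locator Guide form and the HSPC segment were not supplied. An instruction on remote contacts may sit there, so the point cannot be extended to the protocol as a whole.

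Fourth, III(e) requires a 911 call in one case and does not forbid it in others; an attempt seen live on Zoom could reasonably be read as covered. The presence condition on steps already taken is attached to one sentence. Later sentences ask about plans, weapons and pills without repeating it, though removing weapons implies being there. The wording is therefore unclear on remote contacts and does not exclude them.

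**Conclusion.** The point holds for the Appendix III suicide steps as shown and for remote follow-up of women who have moved out of state. For that contact, the steps name one county crisis team, require 911 only for an attempt in the staff member's presence, and contain no instruction to confirm her location, draw on the Locator Guide, or reach a service covering where she is.

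Its size cannot be stated. Section 2.16 expects about 96 women at 6 months, but the documents do not say how many contacts would be remote, and in-person travel is the norm. The conclusion assumes that the unseen material holds no such instruction; if it does, a cross-reference from III(b) would settle the matter.

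Two wider readings are not supported: that a suicidal woman on a call is left without any response, and that a gap has been shown for every woman outside Los Angeles County, including those seen in person. The trial's estimates are unaffected. The change is worth making because it is cheap and directly protects participants.

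**What to change.** - At the start of each Zoom or phone follow-up, confirm and record the participant's current location, a callback number and a local emergency contact, and update the Locator Guide with them.
- Amend III(b)(2) so that, for an out-of-state remote participant, staff give that location to the on-call clinician and contact the emergency or crisis service covering it while she stays on the line.
- State in III(e) that an attempt disclosed or seen by phone or Zoom counts as occurring in the staff member's presence.
- Have staff ask about steps already taken, such as pills, on remote calls too.

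The cost is a short check that may partly repeat the Locator Guide, and a few lines in Appendix III. No extra visits or staff are needed.

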APPENDIX IV: Citations for Study Measures

Primary Outcome:

PTSD Checklist for DSM-5 (PCL-5; Weathers, Litz, Keane, Palmieri, Marx, & Schnurr, 2013). Responses will be scored continuously and according to diagnostic criteria as implemented in previous research.(143) The PCL-5 initially starts with the identification of the presence of exposure to a DSM-V traumatic event (i.e., "Briefly identify the worst event (if you feel comfortable doing so)") and then assesses whether it involved actual or threatened death, serious injury or sexual violence; whether the person directly experienced it (through direct exposure, witness to the event, occurred to a close friend or family member, or exposed as part of job). There are then twenty-items that assess all four B-E criterion (re-experiencing, avoidance, negative thoughts or cognitions, hyperarousal), assessed on a Likert-type scale 0 "not at all", 1 "a little bit", 2 "moderately", 3 "quite a bit", 4 "extremely".

Secondary outcomes:

Substance use:

Self-report drug use: Texas Christian University (TCU) Screen at Baseline and 6-month follow up. Yes/No to each drug will be assessed for use vs dependency. The total score ranges from 0 - 9; higher scores (> 3) correspond to the DSM drug dependence diagnosis. This will be assessed at baseline, immediately following 9th/final intervention session, and 6-month follow-u (Institute of Behavioral Research, 2017).

Objective drug use assessment: A 5-panel FDA-approved urine test cup will be used in this study. The test cup screens for metabolites of the following drugs of abuse at the established cut-off levels and is used for qualitative purposes: Amphetamines (1000 ng/mL), Cocaine (300 ng/mL), Methamphetamines/ MDMA (500 ng/mL), Opiates (2000 ng/mL), and THC (50 ng/mL). Urine sample validity checks will be provided by temperature and adulterant monitoring strips built into the test cup. Participants whose urine does not pass validity checks will be counted as positive for drugs. Results will be coded qualitatively (above or below threshold). All positive results will be interpreted as positive, regardless of self-report.

Depression: will be assessed using the PROMIS measure for depression (Emotional Distress). The 8-tem form will be used. It assesses negative mood, views of self (e.g., worthlessness), decreased positive affect and anhedonia. In self-report when all participants are given the same questions, it is desirable to use the 8-item short form, which has reliability and validity comparable to the 28-item computer adaptive form (PROMIS Health Organization, 2019).

Cortisol reactivity: Saliva samples will be collected via passive drool before and after a modified script driven imagery task. Saliva All saliva will be assayed in duplicate using standard manufacturers protocol (Salimetrics). The concentration of CRP in saliva will be determined using a Salivary C-Reactive Protein ELISA kit, an enzyme-linked immunoassay. The standard curve is run on every assay plate and must have an R2 value of > 0.99. The

replicates must have a %CV < 15 or an absolute difference <0.030 between the replicates. The mean values across saliva duplicates will be computed for each sample and used in the statistical analyses.

C-reactive protein (CRP) All saliva will be assayed in duplicate using standard manufacturers protocol (Salimetrics). The concentration of CRP in saliva will be determined using a Salivary C-Reactive Protein ELISA kit, an enzyme-linked immunoassay. The standard curve is run on every assay plate and must have an R2 value of > 0.99. The replicates must have a %CV < 15 or an absolute difference <0.030 between the replicates. The mean values across saliva duplicates will be computed for each sample and used in the statistical analyses.

Perceived stress scale: 10-item Perceived Stress Scale (PSS) will be used to measure participant's perception of stress (Cohen, 1993).

Quality of life: will be measured using the 10-item short form of the Quality of Life Enjoyment and Satisfaction Questionnaire. Participants indicate their satisfaction with health, finances, and other life domains during the past week on a scale of 0 (very unsatisfied) to 3 (very satisfied) (Endicottt, Nee, Harrison, & Blumenthal, 1993).

Satisfaction with life scale: A 5-item scale designed to measure global cognitive judgments of one's life satisfaction (not a measure of either positive or negative affect) (Diener, Emmons, Larsen, & Griffin, 1985).

Mindful awareness attention scale (MAAS): is a 15-item scale designed to assess a core characteristic of mindfulness, namely, a receptive state of mind in which attention, informed by a sensitive awareness of what is occurring in the present, simply observes what is taking place (Brown & Ryan, 2003; Carlson & Brown, 2005).

Five facet Mindfulness Questionnaire (FFMQ) is a 39 item questionnaire that assesses five independent sub-scales: observing, describing, acting with awareness, non-judging of inner experience, and non-reactivity to inner experience (Baer et al., 2008).

Life event history: Life events history will be assessed by asking respondents whether they ever experienced each of 40 specific negative life events (NLEs; will include both trauma and stressors), and, if so, at what age(s) this occurred. This will also be updated with respect to recent events upon immediate completion of the 9 week courses as well as at the 6-month follow up. The measure was modified from the Diagnostic Interview Schedule trauma section (Robins, Helzer,

Croughan, & Ratcliff, 1981) by including several stressful or traumatic events reported by primary care patients ([name], Silver, & Waitzkin, 2000) and has provided rates of events comparable to other community-based studies (e.g., Seery et al., 2010).

Emotion regulation: will be assessed with the Difficulties in Emotion-Regulation Scale (DERS; Gratz & Roemer, 2004; Kaufman et al., 2016), short form. DERS is a 18- item questionnaire that aims to measure how much one is able to regulate/deregulate their emotions. The 41 questions are based off of six factors including acceptance of emotions, impulsiveness, ability to work towards goals, awareness of own emotions, clarity of emotions, and accessibility to emotion-regulation strategies

Social support will be assessed using the MOS Social Support scale (Sherbourne & Stewart, 1993) This 19 item measure assesses social support.

Anxiety: will be assessed using the PROMIS measure for anxiety (Emotional Distress). The 8-tem form will be used. It assesses symptoms of Generalized Anxiety Disorder. it is desirable to use the 8-item short form, which has reliability and validity comparable to the 28-item computer adaptive form (PROMIS Health Organization, 2019).

General Self-efficacy scale: This 10-item scale was created to assess a general sense of perceived self-efficacy (Schwarzer & Jerusalem, 1995).

Demographics: Age, ethnicity, sexual orientation, incarceration history, religion, income, education, number of children, pregnancy status, mental health history (previous diagnosis) employment history.

Prior Doctor-diagnosed Health Conditions. This survey, modified from the CDC's National Center for Health Statistics Annual National Health Interview Survey, asks respondents to report doctor diagnosed health ailments. This will be assessed at baseline, immediately following 9th/final intervention session, and 6-month follow-up.

Adherence. Measured by class attendance and self-reported time in mindfulness meditation and doing at-home assignment.

Short self-compassion scale. This 12-item scale assesses self-compassion (Raes, Pommier, Neff, & Van Gucht, 2011).

Free Response: Participants will be given the opportunity to provide written feedback regarding their experiences that may not have been captured with these quantitative measures. Prompt will include: We will ask: "Do you have any other thoughts and/or feelings about your participation in this program? Is there anything that you wish to share with us regarding your experience?"

Collection Procedure*

*Please keep a roster of all samples collected from October 2019 onwards. Samples may contain SARS- CoV-2, and this will ensure safe handling in the future as labs may take extra precautions when handling samples collected during this time.

- 1. Participants wash hands for 20 seconds prior to collecting the saliva sample(s).
- 2. Collect saliva sample as normal (follow typical passive drool or swab collection protocols). Tubes should be labeled prior to providing them to participants.
- Sample tubes should be immediately capped and sealed. Outsides of tubes should be disinfected following collection. Disinfectants are listed on the CDC website (https://www.epa.gov/pesticide-registration/list-n-disinfectants-use-against-sars-cov-2). Ensure no disinfectants leak into the tube via an unsealed or partially sealed tube.
- 4. Samples should be placed in a secondary container (sealed plastic bag with absorbent material, freezer box, etc.) that is labeled, then placed in a freezer (-20°C) as soon as possible. See below for more guidelines.
- 5. Participants should wash hands for at least 20 seconds after collecting the saliva sample(s).

Sample Storage and Shipping

Always check with your EHS and IRB groups at your institution before collecting and/or shipping saliva samples to ensure you have received proper training and are following appropriate rules/regulations. Additionally, please refer to the following link for CDC guidelines prior to shipping samples: https://www.cdc.gov/coronavirus/2019-ncov/lab/biosafety-fags.html

Sample storage:

- 1. Once collected, samples should be stored in a freezer between -20°C (home freezer) or -80°C (ultra-cold lab grade freezer) when possible
- 2. Samples should be placed inside sample storage boxes (or biohazard Ziploc bags + absorbent material for home collections)
- 3. The sample storage box should be placed inside a large biohazard Ziploc bag (or Ziploc bag with a biohazard sticker on it)
- 4. A piece of absorbent material (paper towel, etc.) should be placed inside the Ziploc bag to absorb any potential spillageSample Pickup/Shipping:

- 1. Samples in bags or boxes should be placed inside cooler or in a bioshipper on dry ice.
- 2. Bioshipper should be labeled with the following:
 - a. Hazard labeled with UN Identification Number already on label UN 3373
 - b. Biological Substance, Category B
 - c. Hazard Labeled with UN Identification Number- UN 1845
 - d. Dry Ice along with the net weight (kg) of the dry ice
 - e. Shipper's name and address
 - f. Receiver's name and address
 - g. Name and phone number of a responsible person.

Receiving samples:

- 1. Lab personnel receiving samples should wear appropriate PPE before handling samples.
- 2. Ensure samples are labelled, are frozen, and tubes are in good condition (no cracks or leaks).
- 3. Sample collection tubes should be disinfected once received by the lab. Disinfectants are listed on the CDC website (https://www.epa.gov/pesticide-registration/list-n-disinfectants-use-against- sars-cov-2).
- 4. Boxes with samples can be marked with date received, and a label noting if the samples were collected during the COVID-19 pandemic. This can act as an indicator to use extra safety precautions while handling those samples in the future. Samples should be stored in -80°C as soon as possible.
- 5. Sample processing should be performed in a biological safety cabinet.

APPENDIX VII: RECap for Screener (Section 1) and Baseline, Immediate-follow-up, and 6-months (Section 2)

MINDFULNESS-BASED INTERVENTION FOR TRAUMA-EXPOSED, HOMELESS WOMEN

STUDY PROTOCOL

